In addition, the primary safety and efficacy variables will be analysed descriptively for the following groups:

- each osocimab group, placebo high dose group, placebo low dose group,
- pooled osocimab group, pooled placebo group.

For the primary analysis and all analyses conducted at primary completion which will occur once the last patient completed the end of main treatment phase visit, only the main treatment period will be considered. The partial data of a subject’s extended treatment period up until primary completion may be presented in separate tables.

At full study completion, also the extension treatment and follow-up period will be considered.

Incidence rates and cumulative incidences will be calculated only for endpoints with at least 3 events in at least one treatment arm. Hazard ratios (cause specific and subdistribution) will be calculated only if in addition at least 1 event in each of the compared treatment arm occur.

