6.4 Safety

6.4.1 Primary safety variables

The composite of major bleeding (MB) and clinically relevant non-major bleeding (CRNMB) events, as assessed by CIAC, and the composite of moderate and severe AEs and SAEs will

be the primary safety endpoints in this study. Only events that started after the first dose of study treatment and during the main treatment period are considered for the primary analysis.

For the primary safety analysis descriptive time to first primary safety event (both treatment emergent AEs and composite of treatment emergent major and CRNMB events [in alignment with ISTH guidelines]) analyses will be performed.

According to the description of the primary estimand, the following events will be considered as competing events for the respective safety endpoint:

- death
- premature end of exposure to assigned treatment (last administration of assigned treatment plus 30 days).

For the primary analysis, the time to event for a subject will be censored at the date of the EOMT visit or after no further data collection happened for a subject (e.g. lost to follow-up).

According to the study protocol (section 7.1.1) one maintenance dose can be missed. If a subject misses a maintenance dose, has a so called administration gap, that lasts longer than 30 days, the subject is not considered at risk for treatment-emergent events during this time until the next dose. When the subject then takes a maintenance dose again, he/she is at risk again. Accordingly there will be additional analyses, where the time not under exposure between two doses will be ignored and events during that time will not be counted. The time under risk will be calculated by removing time between the interrupted dose + 30 days and the next dose and the time more than 30 days after permanent discontinuation to study drug and if occurred the 1st event per patient will be counted. For the primary analysis in this data scope, the time to event for a subject will be censored at the date of the EOMT visit or after no further data collection happened for a subject (e.g. lost to follow-up).

The cumulative incidence function for the event-of-interest as well as the associated competing event(s) together with the corresponding confidence interval will be estimated for each treatment arm using Aalen-Johansen estimators.

The competing event for the primary safety endpoint is death and premature discontinuation of exposure to assigned treatment.

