The cumulative incidence, i.e. the probability of having a specific event E at or before a timepoint t, $P(T \leq t, E = 1)$, will be estimated for time-to-event endpoints by Aalen-Johansen estimators with the competing event.

The difference of the Aalen-Johansen estimators between high dose osocimab and placebo and low dose osocimab and placebo will be presented with a 90% confidence interval.

As the Aalen-Johansen estimator is approximately normal distributed (Aalen, Borgan and Gjessing 2008), the difference of Aalen-Johansen estimators is approximately normal distributed. Thus, the two-sided 90% confidence interval is obtained via:

$$\left[\widehat{AJ}^{TRT}(day) - \widehat{AJ}^{CON}(day) \pm z_{0.95} \sqrt{\sigma^2(\widehat{AJ}^{TRT}(day)) + \sigma^2(\widehat{AJ}^{CON}(day))} \right],$$

with $\widehat{AJ}^{TRT}(day)/\widehat{AJ}^{CON}(day)$ the Aalen-Johansen estimator for treatment TRT/ control CON at study day, $z_{0.95}$ the 90% quantile of the standard normal distribution and $\sigma^2(\widehat{AJ}^{TRT}(day))$ and $\sigma^2(\widehat{AJ}^{CON}(day))$ the estimated variance of the Aalen-Johansen

estimator for osocimab (treatment, TRT) and placebo (control, CON) at study day, estimated with the Aalen method.

Rates

Cause-specific incidence rates will be calculated for each treatment arm with an 90% confidence interval.

The exposure-adjusted incidence rate will be expressed a “subjects with an event – per 100 participant years”. For that the following formula is used:

$$IR_{adj} = \frac{\#Participants\ with\ an\ event}{\sum\ time\ under\ treatment\ (in\ days)/(100 * 365.25)}$$

The 90% confidence interval for the exposure-adjusted IR will be computed as

$$\left[\frac{IR_{adj} * \chi^2(0.05; 2e)}{2e}, \frac{IR_{adj} * \chi^2(0.95; 2e)}{2e} \right],$$

with $\chi^2(q; 2e)$ the q quantile of a chi square distribution with 2e degrees of freedoms and e the number of participants with an event. (Nelson 1982)

With respect to the cause-specific hazards for the respective safety variable, each of the osocimab groups will be compared to the placebo group using two-sided log-rank tests at a type I error rate of $\alpha=10\%$. Due to the explorative nature of these analyses, no multiplicity adjustment will be done.

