6.4.3 Other safety analyses

All Bleedings Analysis

The primary safety analyses will be repeated for all bleedings (defined as the composite of MB, CRNMB and minor bleedings) and its components for the safety analysis set.

Bleeding analysis by ISTH category

The descriptive primary safety analysis will be repeated for all major bleedings and their respective ISTH categorization.

BARC Bleedings Analysis

The descriptive primary safety analyses will be repeated for bleeding types 1 to 5, including any sub types, according to the BARC Bleeding Criteria. These are defined as follows:

- Type 0:
 - No bleeding
- Type 1:
 - Bleeding that is not actionable and does not cause the patient to seek unscheduled performance of studies, hospitalization, or treatment by a health-care professional; may include episodes leading to self-discontinuation of medical therapy by the patient without consulting a health-care professional.
- Type 2:
 - Any overt, actionable sign of hemorrhage (e.g., more bleeding than would be expected for a clinical circumstance, including bleeding found by imaging

alone) that does not fit the criteria for type 3, 4, or 5 but does meet at least one of the following criteria:

- requiring nonsurgical, medical intervention by a health-care professional,
 - leading to hospitalization or increased level of care, or
 - prompting evaluation
- Type 3:
 - Type 3a:
 - Overt bleeding plus hemoglobin drop of 3 to < 5 g/dL* (provided hemoglobin drop is related to bleed)
 - Any transfusion with overt bleeding
 - Type 3b:
 - Overt bleeding plus hemoglobin drop ≥ 5 g/dL* (provided hemoglobin drop is related to bleed),
 - Cardiac tamponade,
 - Bleeding requiring surgical intervention for control (excluding dental/nasal/skin/hemorrhoid),
 - Bleeding requiring intravenous vasoactive agents
 - Type 3c:
 - Intracranial hemorrhage (does not include microbleeds or hemorrhagic transformation, does include intraspinal),
 - Subcategories confirmed by autopsy or imaging or lumbar puncture,
 - Intraocular bleed compromising vision.
 - Type 4:
 - CABG-related bleeding,
 - Perioperative intracranial bleeding within 48 h,
 - Reoperation after closure of sternotomy for the purpose of controlling bleeding
 - Transfusion of ≥ 5 U whole blood or packed red blood cells within a 48-h period,
 - Chest tube output more than or equal to 2L within a 24-h period
 - Type 5:
 - Fatal bleeding
 - Type 5a:

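### SAP 6.4.1 uses 2e degrees of freedom in both limits of the 90% CI for the incidence rate although follow-up ends by time: the upper limit is about 8% too low at the planned bleeding count, more for rarer outcomes, and undefined for a zero-event arm

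*SAP*

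**What the plan says.** SAP 6.4.1, under Rates, states: "Cause-specific incidence rates will be calculated for each treatment arm with an 90% confidence interval". The rate is the number of participants with an event divided by the summed time under treatment, scaled to 100 participant-years. The limits follow "The 90% confidence interval for the exposure-adjusted IR will be computed as": the rate times the 0.05 chi-square quantile over 2e, and the rate times the 0.95 quantile over 2e, with "the q quantile of a chi square distribution with 2e degrees of freedoms and e the number of participants with an event". Both limits therefore use 2e degrees of freedom.

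The same section ends observation by time: "the time to event for a subject will be censored at the date of the EOMT visit", or when data collection for the subject stops.

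The opening text of SAP Section 6 sets the reporting rule: "Incidence rates and cumulative incidences will be calculated only for endpoints with at least 3 events in at least one treatment arm". The further condition of at least one event in each compared arm applies only to hazard ratios. The same text asks for the primary variables to be shown for "each osocimab group, placebo high dose group, placebo low dose group". SAP 6.4.3 extends the analysis to rarer outcomes, including BARC types: "The descriptive primary safety analysis will be repeated for all major bleedings and their respective ISTH categorization".

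In the confidence interval for the Aalen-Johansen difference, z_0.95 is described as "the 90% quantile of the standard normal distribution".

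**The concern.** The 2e/2e pair is the exact interval when follow-up runs until a fixed number of events has occurred. When follow-up ends by time, e is approximately Poisson. The exact lower limit still uses 2e, but the exact upper limit uses 2e+2. The error therefore runs in one direction: it understates how high the rate could still be.

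That is the limit that matters for safety. Protocol 9.1 makes the primary objective a qualitative assessment of safety with descriptive analyses and no formal hypothesis, so readers will judge an arm's bleeding risk partly from its interval. The shortfall grows as counts fall: in the two placebo cohorts shown separately, in the ISTH categories of major bleeding and in the BARC types. With e = 0 the formula divides by zero, and the SAP gives no fallback.

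**Working it through.** **Inputs.** From SAP Section 3: 200 participants in each osocimab group and 200 on placebo, the latter split into two cohorts of 100. From SAP 9.1: 10 bleeds per 100 patient-years, hazard ratio 1.0, 6 months of treatment, and 15 lost to follow-up per 100 patient-years.

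**The plan's own figure.** SAP 9.1 expects 555 of 600 to complete: 600 × (1 − 0.15 × 0.5) = 555. This reproduces. The SAP gives no worked value for the rate interval and no event count.

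**Expected count per group.** With constant hazards of 0.10 and 0.15 per year over 0.5 years:
- person-years = 200/0.25 × (1 − exp(−0.125)) = 94.0
- bleeds = 0.10 × 94.0 = 9.40
- a placebo cohort of 100: 4.70 bleeds

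**Upper limits.** SAP: χ²(0.95; 2e)/2 divided by person-years. Exact Poisson: χ²(0.95; 2e+2)/2 divided by person-years. The rates below use 94.0 person-years.

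| e | Events, 2e | Events, 2e+2 | Per 100 PY, 2e | Per 100 PY, 2e+2 | SAP too low by |
|---|---|---|---|---|---|
| 9 | 14.43 | 15.71 | 15.36 | 16.71 | 8.1% |
| 5 | 9.15 | 10.51 | 9.74 | 11.18 | 12.9% |
| 3 | 6.30 | 7.75 | 6.70 | 8.25 | 18.8% |
| 1 | 3.00 | 4.74 | 3.19 | 5.05 | 36.9% |
| 0 | none | 3.00 | none | 3.19 | – |

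The value for e events with 2e equals the value for e−1 events with 2e+2 (compare e = 1 and e = 0). For the adverse event composite, taking 60 to 140 events per arm as an assumption, the shortfall is 1.5% to 0.7% (73.28 against 74.39; 160.01 against 161.08).

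**Coverage.** I simulated the time-censored design: exponential bleeds and losses, administrative censoring at 0.5 years, person-time to first event or censoring, 200,000 trials per size. Nominal values are 90% coverage and 5% with the true rate above the upper limit.

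| Participants | Coverage, 2e | True rate above limit, 2e | Coverage, 2e+2 | True rate above limit, 2e+2 |
|---|---|---|---|---|
| 200 | 87.5% | 8.7% | 92.3% | 3.9% |
| 100 | 84.8% | 10.9% | 92.0% | 3.6% |

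Coverage for counts is saw-toothed, so a single mean can mislead. Exact Poisson sums averaged over means 8 to 11 give 88.6% and 7.6% with 2e, and 92.9% and 3.4% with 2e+2.

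**Zero-event arm.** Take three groups with equal Poisson means. The probability that at least one group has no event while at least one has 3 or more is 0.02% at a mean of 9.4, 12% at 3 and 20% at 2. The means of 2 and 3 are assumptions for rarer outcomes; the SAP gives no rates for these.

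**The case against.** The strongest reply is that 2e+2 is a conservative bound, not a calibrated one. Against the mid-P Poisson limit the shortfall is 4.7% at e = 9, 7.9% at 5 and 12.1% at 3, while the 2e+2 limit is 3.7%, 5.8% and 8.3% too high. On two-sided coverage averaged over means 8 to 11, the SAP interval (88.6%) is nearer 90% than the replacement (92.9%). Over means 4 to 6 the figures are 87.8% and 94.2%, so 84.8% for a placebo cohort is a low point on the saw-tooth.

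This stands as a caution on size, and part of the choice is a preference for guaranteed coverage. It does not rescue the printed limit. Even the mid-P benchmark finds it too low, and the misses above the upper limit exceed 5% on average. For a bleeding rate, that is the wrong side on which to err.

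The planned count is also derived, not stated. The width of the hazard ratio interval in SAP 9.1, [0.57; 2.28], implies about 11.3 events per group: ln(2.28/0.57) = 1.386, the standard error is 1.386/(2 × 1.645) = 0.421, and 2/0.421² ≈ 11.3. At 11 events the shortfall is 6.8%, so the conclusion does not change. The 9.4 figure also ignores the competing events (death and premature end of exposure).

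The estimand's summary measure is the cause-specific hazard ratio, Aalen-Johansen estimates also give absolute risk, and no stated decision rests on a single-arm rate. All of this is true, and it limits the seriousness. The zero-event case is negligible for the bleeding composite. SAP 6.4.1 cites a textbook for the formula; it was not available to check whether the formula is offered there as an approximation.

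**Conclusion.** The concern holds. As printed, the upper limit of the 90% interval is too low for a time-ended study: by 8.1% at 9 events, 12.9% at 5 and 18.8% at 3 against the exact Poisson limit, and by 4.7%, 7.9% and 12.1% against mid-P. It has no value for a zero-event arm. These percentages depend only on e. The planned count of about 9.4 rests on constant hazards, the SAP's planning rates and no competing events.

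The point should be fixed, but it is confined to the incidence-rate intervals. The lower limits for arms with events, hazard ratios, log-rank tests, Aalen-Johansen estimates and the sample size are unaffected, and the adverse event composite barely moves. Two wording points nearby carry no weight in this conclusion. The denominator, time under treatment, is not defined for the primary rate (no direction of bias is claimed). The z_0.95 label is a slip, because the printed formula already gives a 90% interval.

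**What to change.** In SAP 6.4.1, Rates:
- Keep the lower limit as χ²(0.05; 2e)/2 divided by person-time, and set it to 0 when e = 0.
- Compute the upper limit as χ²(0.95; 2e+2)/2 divided by person-time. At e = 0 this gives 3.00 divided by person-time.
- State that person-time runs from first dose to first event, competing event or censoring, whichever comes first.
- Relabel z_0.95 as the 95% quantile of the standard normal distribution.

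The cost is one formula, one zero-event rule, one sentence, one label and a rerun of the rate tables. SAP 6.5 indicates that the primary analysis was already complete, so its rate tables are included. Because the change would come after the unblinding described in SAP 4.4, the study report should record it as a correction and show the prespecified limits alongside. The statistical price is slightly wider intervals, with about 92–93% coverage at the planned count.

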## 6.3 Measures to Minimize Bias: Randomization and Blinding

After a participant has signed an informed consent form, the unique participant identification number (PID) will be assigned via Interactive Web Response System (IWRS). If a participant is re-screened, a new PID will be assigned. The PID is a 9-digit number consisting of:

Digits 1 to 5 = Unique site number

Digits 6 to 9 = Unique participant number (current participant number within the study site)

The unique participant number will start with 5 for each participant.

All participants will be centrally assigned to randomized study intervention using an IWRS. Study intervention will be administered at the study visits summarized in SoA (Section 1.3). Before the study is initiated, the log in information and directions for IWRS will be provided to each site.

Covariate-adaptive randomization techniques (minimization methods) will be utilized taking into account the following baseline covariates (weights of the baseline covariates for the calculation of imbalance in brackets):

- Region (categorical) (17.0%)
- Age (17.0%)
- Prior major adverse cardiovascular event (MACE) (17.0%)
- Dialysis access via catheter (17.0%)
- Low-dose ASA use (Yes/No) (17.0%)
- Diabetes (Yes/No) (7.5%)

- Atrial fibrillation (Yes/No) (7.5%)

Sponsor, participants and investigators are being blinded with respect to active treatment versus placebo, but not blinded to dose cohort (low or high dose). The CIAC will be blinded to the participant's treatment allocation and dose cohort. The DMC will review blinded data and will have access to unblinded data as outlined in the DMC charter.

In order to maintain the blind, osocimab and matching placebo will be packaged in identical vials and each vial will be labeled with a unique, pre-printed number.

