## **9. Statistical Considerations**

### **9.1 Statistical Hypotheses**

The primary objective of this study is a qualitative assessment of safety. All analyses are performed in a descriptive manner and thus no formal hypothesis is defined.

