For the analysis of the primary endpoint in this study, the hazard function  $h(t)$  is the chance that an individual experiences an event of the primary safety outcome in the next instant in time, given that the individual has not had such an event up to time  $t$ . For example, for the comparison of the osocimab high dose group with the placebo group, the corresponding Cox proportional hazards model can be described by the following equation:

$$h(t, x_i) = h_0(t) \exp(\beta x_i),$$

where

- $h(\cdot)$  hazard function for primary safety outcome, as a function of time and participant's covariates
- $h_0(\cdot)$  unspecified underlying baseline hazard function for primary safety outcome; hazard of an individual with  $x_i = 0$
- $t$  time (in days) relative to the date of first study intervention
- $x_i$  treatment group of participant  $i$   
(0 corresponds to "placebo group" and  
1 corresponds to "osocimab high dose group")
- $\beta$  unknown parameter (to be estimated); hazard ratio =  $\exp(\beta)$

Only events that started after the first dose of study treatment and during the main treatment period are considered for the primary analysis. Events that occurred during the pre-treatment period will be displayed in an exploratory manner.

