3.1 Randomization and Blinding

Subjects will be randomized between osocimab low dose and placebo low dose and osocimab high dose and placebo high dose in a ratio of 2:1:2:1. Covariate-adaptive randomization techniques, or better the Pocock and Simon Minimization with Biased-coin Assignment methodology (Pocock, SJ, R Simon. ‘Sequential treatment assignment with balancing for prognostic factors in the controlled clinical trial’, Biometrics, 31, pp 103–115, 1975) will be utilized to perform subject randomization for this study.

In brief, each subject’s randomization is performed by calculating the imbalance that will exist by assigning each treatment group in turn – by considering the previous treatment assignments to pre-specified balancing factor levels corresponding to the subject being randomized, and summing the individual factor level imbalances to determine which treatment(s) have minimal imbalance. The treatment assignment for this subject is then performed in a non-deterministic manner, by assigning probabilities of treatment assignment to each of the treatment arms based on the calculated treatment imbalances.

More detailed information can be found in sections 9.2, 9.3 and in the Covariate Adaptive Randomization User Requirements Specification (CARURS) as provided by the IwRS provider ALMAC Clinical Technologies.

The following baseline covariates will be taken into account:

- Region (categorical)
- Age (<50yrs/>=50-<60yrs/>=60-<65yrs/>=65-<70yrs/>=70-<80yrs/>=80yrs)
- Prior major adverse cardiovascular event (MACE) (Yes/No)
- Dialysis access via catheter (Yes/No)
- Low-dose ASA use (Yes/No)

- Diabetes (Yes/No)
- Atrial fibrillation (Yes/No)

The first five covariates will have twice the factor weight than the latter two.

Sponsor, subjects, and investigators are being blinded with respect to active treatment versus placebo, but not blinded to dose cohort (low or high dose). In order to reduce any risk which could be associated with the open-label nature of the dose cohort, the final SAP will be available before first patient first visit. No ad hoc interim analyses comparing the treatment effect of the two dose cohorts will be performed. Aggregation of treatment-specific interim results will only be performed for safety measures in the context of DMC meetings.

The CIAC will remain blinded to the subject's treatment allocation and dose cohort throughout the course of the study. The DMC is unblinded.

4. General Statistical Considerations

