Cause-specific hazard ratios, cause-specific relative hazard reduction (csRHR; $csRHR = 100 \times [1 - \text{cause-specific hazard ratio}]\%$), and corresponding 2-sided 90% and 95% confidence intervals, comparing the hazards for the event-of-interest in each of the osocimab groups with the placebo group will be estimated based on two separate cause-specific Cox proportional hazards models. Censoring will be assumed independent of the randomized group assignment.

To complete the analysis, cause-specific HRs will be estimated for (each of) the competing events.

For the analysis of the primary endpoint in this study, the cause-specific hazard function $h_k(t)$ is the chance that an individual experiences an event of the primary safety outcome in the next instant in time, given that the individual has not had such an event or a competing event up to time t. For example, for the comparison of the osocimab high dose group with the placebo group, the corresponding cause-specific Cox proportional hazards model can be described by the following equation:

$$H_k(t, x_i) = h_{0,k}(t) \exp(\beta_k x_i),$$

where

$h_k(\cdot)$ cause-specific hazard function for primary safety outcome, as a function of time and subject's covariates

$h_{0,k}(\cdot)$ unspecified underlying baseline hazard function for primary safety outcome; hazard of an individual with $x_i = 0$

t time (in days) relative to the date of first administration

x_i	treatment group of subject i (0 corresponds to “placebo group” and 1 corresponds to “osocimab high dose group”)
β_k	unknown parameter (to be estimated); cause-specific hazard ratio = $\exp(\beta_k)$
k	type of event

Probability

As a supportive analysis, the cumulative incidence functions for the respective event-of-interest will be compared using the Fine and Grays subdistribution hazards model as well as using the Gray’s test.

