6.4.2 Supplementary Safety Analysis

The primary safety analyses will be repeated for the overall treatment period for the safety analysis set. Here, all events which occurred during the main and extension treatment period will be taken into account. Therefore, a subject will be censored after a primary safety event occurred, or after the date of the EOET visit, or 30 days after study drug discontinuation or after no further data collection happened for a subject (e.g. lost to follow-up).

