 - Imbalance_C: $\text{Max} (\text{Range}[r_B * r_C * r_D * (n_A), r_A * r_C * r_D * (n_B)], \text{Range}[r_B * r_C * r_D * (n_A), r_A * r_B * r_D * (n_C+1)], \text{Range}[r_B * r_C * r_D * (n_A), r_A * r_B * r_C * (n_D)], \text{Range}[r_A * r_C * r_D * (n_B), r_A * r_B * r_D * (n_C+1)], \text{Range}[r_A * r_C * r_D * (n_B), r_A * r_B * r_C * (n_D)], \text{Range}[r_A * r_B * r_D * (n_C+1), r_A * r_B * r_C * (n_D)]) * \text{<factor weight>}$
 - Imbalance_D: $\text{Max} (\text{Range}[r_B * r_C * r_D * (n_A), r_A * r_C * r_D * (n_B)], \text{Range}[r_B * r_C * r_D * (n_A), r_A * r_B * r_D * (n_C)], \text{Range}[r_B * r_C * r_D * (n_A), r_A * r_B * r_C * (n_D+1)], \text{Range}[r_A * r_C * r_D * (n_B), r_A * r_B * r_D * (n_C)], \text{Range}[r_A * r_C * r_D * (n_B), r_A * r_B * r_C * (n_D+1)], \text{Range}[r_A * r_B * r_D * (n_C), r_A * r_B * r_C * (n_D+1)]) * \text{<factor weight>}$

STEP 2:

Calculate the Total Imbalance value for each treatment arm by summing the calculated Treatment Imbalance values for that treatment arm over each of the factor levels.

STEP 3:

Determine the Minimum Imbalance value across the calculated Total Imbalance values for each treatment arm, and which of the treatment arm(s) have this Minimum Imbalance value.

STEP 4:

Based on Table 4.3 (below), assign a Treatment Assignment Probability to each treatment arm; the assigned probabilities are determined by the total number of treatment arms sharing the Minimum Imbalance value and each treatment Total Imbalance value.

The IXRS performs the Probabilistic Treatment Assignment by utilizing a Random Numbers List (generated by Almac – see Section 6) which contains generated random numbers between 0 and 1. For each subject’s randomization, the next available random number from the Random Numbers List is allocated to the subject. Based on the associated random number ranges in Table 4.3, the treatment assignment is made by determining the range within which the allocated random number for that subject lies.

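### Allocation is minimised on seven factors but no AE/SAE analysis adjusts for them; if the factors are prognostic and events common, the 10% log-rank test and its intervals are somewhat conservative

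*SAP*

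**What the plan says.** **Allocation.** Protocol 6.3: "Covariate-adaptive randomization techniques (minimization methods) will be utilized taking into account the following baseline covariates", namely region, age, prior MACE, catheter access, low-dose ASA, diabetes and atrial fibrillation. SAP 3.1 adds: "The first five covariates will have twice the factor weight than the latter two". In Step 4 of SAP 9.2, "the assigned probabilities are determined by the total number of treatment arms sharing the Minimum Imbalance value" and by each arm's total imbalance. The table in SAP 9.3 gives a total probability of 0.85 to the arm or arms with least imbalance, unless all four tie, and shares the other 0.15 among the rest in proportion to the 2:1:2:1 ratio.

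**Analysis.** Under SAP 6.4.1 each dose group is "compared to the placebo group using two-sided log-rank tests at a type I error rate of" 10%, with no strata named. The hazard ratios "will be estimated based on two separate cause-specific Cox proportional hazards models". In Protocol 9.4.2 "the corresponding Cox proportional hazards model can be described by the following equation", and both that equation and the SAP's have one covariate, the treatment group. The Fine and Gray model and Gray's test are listed without covariates.

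**Elsewhere.** SAP 6.4.2: "The primary safety analyses will be repeated for the overall treatment period for the safety analysis set". This changes the period, not the model. The safety subgroups in SAP 6.4.4 cover the bleeding composite only. SAP 2 allows selected analyses to be repeated by COVID-19 status, which is not a balancing factor. Protocol 9.1 limits the weight of all this: "All analyses are performed in a descriptive manner and thus no formal hypothesis is defined".

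**The concern.** Minimisation makes the arms more alike on the seven factors than chance would. If the factors predict AE/SAE events, the unadjusted treatment comparison varies less from trial to trial than under simple randomisation. The ordinary log-rank and Cox variance formulas do not reflect this. The stated standard error is then too large, the nominal 10% test rejects less often than 10% under no effect, and the intervals are too wide.

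For a safety endpoint this cuts both ways: an increase in risk is slightly harder to flag, and slightly harder to rule out. A reader of the results would take the stated 10% level and the 90% and 95% limits at face value.

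**Working it through.** **Inputs from the documents.** N = 600, with 200 per dose and 200 pooled placebo; 2:1:2:1 minimisation with 0.85/0.15 coin and weights 2,2,2,2,2,1,1 (SAP 3.1, 9.2, 9.3); 6 months; loss to follow-up 15 and bleeding 10 per 100 patient-years (SAP 9.1); two-sided 10% test.

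**Inputs not in the documents (assumed).** AE/SAE event proportion, prognostic strength and prevalence of the factors.

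**The plan's own figures.** Completers: 600 x (1 - 0.15 x 0.5) = 555, as stated. The stated bleeding interval [0.57; 2.28] is matched closely by simulation for 400 pooled osocimab v 200 placebo, [0.575; 2.267], and not for one dose, 200 v 200, [0.511; 2.534]. That is a separate matter. The plan states no actual test level under minimisation.

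**Mechanism.** If the log-rank statistic has true standard deviation s instead of 1, the actual level is 2 x [1 - Φ(1.645/s)].
- Simulated s = 0.9567 (factor HR 1.4, 50% events): 1.645/0.9567 = 1.719, level 8.6%; direct count 8.7%.
- Simulated s = 0.9285 (factor HR 1.5, 70% events): 1.645/0.9285 = 1.772, level 7.6%; direct count 7.6%.
- In reverse, a level of 8.6% means 1 - (1.645/1.717)² = 0.082, so the balanced factors carry about 8% of the score variance.

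**Simulated level of the unadjusted test (%).** Three sets, each coding SAP 9.2 and 9.3 directly.

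| Assumed factors | Set A, 35-65% events | Set B, 30-85% events | Set C, about 50% events |
|---|---|---|---|
| Non-prognostic | 10.1-10.3 | about 10 | 10-10.7 |
| Weak | 9.7-9.8 | - | 9.9 |
| Modest (HR 1.25-1.3 each) | - | 8.9-9.4 | - |
| Moderate (B: HR 1.4-1.5 each) | 8.2-9.1 | 7.5-9.1 | 8.4 |
| Strong (B: HR 2.0 each) | 6.9-7.2 | 5.1-7.3 | 7.4 |
| Control: simple randomisation | 9.6-10.6 | 10.0-10.2 | 9.8-10.3 |

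In set A, weak means HRs of 1.08 to 1.25 for the binary factors, up to 1.15 across regions, and 1.5 for oldest v youngest age class. Moderate squares these and strong cubes them. Prevalences in A: region 30/45/25%, age classes 15/20/15/15/25/10%, MACE 35%, catheter 20%, ASA 45%, diabetes 45%, AF 12%. In B: region 25/45/30%, MACE 25%, ASA 40%, the others as in A. Monte Carlo standard errors in A and B are about 0.2-0.3 points per cell. Protocol 6.3 gives weights of 17.0% and 7.5% where the SAP gives 2:1; with moderate factors and 50% events the level is 8.2% either way.

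**Intervals (set A).** The model standard error exceeds the true one by 0-1% (weak), 2-6% (moderate) and 9-11% (strong). Each 90% limit then lies too far out by 0-0.2%, 0.7-1.4% and 2.1-2.4%.

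**Power lost to the sub-nominal level, HR 1.4 (set A).** 0.2-0.3 points (weak), 1.4-3.1 points (moderate).

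**Adjusted test on minimised data.** 10.2-11.2% in set A. In set B it was 10.1-10.7%, against 8.0-8.4% unadjusted on the same data.

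**Bleeding.** Events per dose comparison at HR 1: 400 x 10/25 x (1 - exp(-0.25 x 0.5)) = 18.8. The level was 10.0% with moderate factors in set A, 9.7-10.3% at factor HR 1.4-1.5 in set B, and about 9% at HR 2.0.

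**The case against.** The strongest case is that this is a refinement the trial can do without.
- The analyses are descriptive and unadjusted for multiplicity. Two doses and two composites give four tests; if independent, the chance of at least one false positive is 1 - 0.9⁴ = 34%. One or two points on one test hardly matter beside that.
- With 200 events a 90% limit already lies a factor exp(1.645 x 2/√200) = 1.26 from the HR, so a shift of about 1% is small.
- With weak factors the unadjusted test is about 0.2 points off nominal and the adjusted test further off, on the other side.
- The primary analysis is complete and unblinding (SAP 4.4, 6.5), so an added analysis is post hoc, and SAP 4.5 already permits post-hoc work in general terms.
- SAP 7.2 records that stratified sensitivity analyses were removed in version 2.0.

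Most of this stands and limits the weight of the point. It does not remove the mismatch between the stated 10% level and the level the design is likely to deliver with prognostic factors. A general permission names no adjusted analysis. The point rests on the current text, not on the earlier removal.

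A reader might also infer that minimisation pulls the hazard ratio towards 1 and so hides harm. The calculations do not support this. At a conditional HR of 1.4 with moderate factors, the mean unadjusted HR is 1.35-1.38 under minimisation and 1.36-1.38 under simple randomisation. The difference from 1.4 is non-collapsibility, and the documents set no conditional target. Likewise, the adjusted model's power gain with its level set to exactly 10% (2.4-4.3 points, moderate factors) is much the same under simple randomisation (1.8-4.2). It overlaps with the power loss given above and must not be added to it.

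**Conclusion.** The point holds in direction and mechanism. No analysis of the AE/SAE composite adjusts for, or stratifies by, the factors that drove allocation. If those factors are prognostic and the events common, the test and the intervals are conservative. The actual level is about 10% with non-prognostic factors, 9-10% with weak ones, roughly 7.5-9.4% with modest to moderate ones and about 5-7.5% with strong ones. All of these rest on assumed event proportions, prevalences and factor effects.

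A reader might take one central value, such as the 8.6% that moderate factors give when set A is pooled over event rates, as the level of this trial's test. The documents give no event rate, prevalence or prognostic strength from which to fix such a figure. Nor do they support calling the primary analysis invalid: the error is on the conservative side, no decision rests on the test, and incidence rates and Aalen-Johansen differences are reported too. The intervals for those differences also use variances that ignore the balancing, so the same reasoning applies to them, though this was not simulated. Bleeding needs no change at the planned rate. The consequence is modest, and the change is worth making because it is cheap.

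**What to change.** In SAP 6.4.2, for the AE/SAE composite in the main treatment period and the safety analysis set, add a supportive cause-specific Cox model for each osocimab dose v pooled placebo, with treatment plus all seven minimisation factors as coded in the IWRS (age classes as in SAP 3.1). Using all seven as coded leaves no covariate choice after unblinding. Report its hazard ratio, labelled conditional, with 90% and 95% intervals and test, beside the unadjusted result. Label the analysis as added after the primary analysis. State there that the unadjusted test and intervals, including those for the Aalen-Johansen differences, are conservative under minimisation if the factors are prognostic.

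Keep the primary model, the protocol equation and the estimand unchanged, and leave the bleeding composite unadjusted.

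The cost is one SAP paragraph and one table row per dose, with no new data, since allocation already uses these factors. The downside should be named in the text: a second hazard ratio with a different target, and an adjusted test slightly above nominal, at about 10-11%.
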